Evaluation of Cardiovascular Disease Risk in Children with Type 1 Diabetes Mellitus by Oscillometric Method and Echocardiography

Statistical analysis

All analyses were carried using SPSS 25.0 (IBM, USA). The findings of the study are expressed as frequency and percentages. Normality test was conducted using the Kolmogorov-Smirnov test. Non-normally distributed variables were presented as the median and interquartile range (IQR) with 25^{th} – 75^{th} percentiles, while variables with normal distribution are expressed as mean \pm standard deviation. Categorical variables were compared using the Chi-square test. Fischer's exact test was applied according to the percentage of expected counts. Numerical variables with and without normal distribution were compared using the independent samples t-test and Mann–Whitney U, respectively. The Kruskal–Wallis test was used to compare numerical variables without normal distribution between more than two groups. Spearman correlation analysis was performed to determine the variables associated with EFT, cIMT, AIx@75, and PWV scores and p<0.05 was considered as a statistically significant value. Multivariable logistic regression analysis was performed to detect associated factors with PWV and AIx@75.

Study Protocol

Participants of this cross-sectional, single-center study were recruited from Pediatric Endocrinology department. T1DM patients with a body mass index (BMI) between the 5th and 85th percentile according to age and gender, having this diagnosis for at least 2 years and ages 8–18 years, were consecutively included in the study. Exclusion criteria for the patient were determined to be having any chronic diseases other than T1DM and presence of a congenital and/or acquired heart disease, hypertension etc. Healthy adolescents were recruited from those who applied to the pediatric clinic for annual routine child health check-ups and were healthy. The control group consisted of 87 sex, age and BMI matched healthy children. Exclusion

criteria for the control group were determined to be having any chronic diseases and presence of a congenital and/or acquired heart disease, hypertension etc. Each subjects weight, height measurements were done and BMI was estimated.

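### Years since T1DM diagnosis appear only as an entry cut-off; no stated analysis is committed to estimating how the patient-control difference changes with duration, or to adjusting the comparison for age

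*Combined protocol and SAP*

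**What the plan says.** Duration of T1DM is named once in the combined protocol and SAP. Under Study Protocol, patients "having this diagnosis for at least 2 years and ages 8–18 years, were consecutively included in the study". The minimum is 2 years and no maximum is given. The same section describes the comparison group: "The control group consisted of 87 sex, age and BMI matched healthy children". The number of patients is not stated.

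The Statistical analysis section lists four tools that bear on the markers:

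- Two-group comparison: "Numerical variables with and without normal distribution were compared using the independent samples t-test and Mann–Whitney U, respectively".
- More than two groups: "The Kruskal–Wallis test was used to compare numerical variables without normal distribution between more than two groups". The groups are not defined.
- Correlation: "Spearman correlation analysis was performed to determine the variables associated with EFT, cIMT, AIx@75, and PWV scores". The candidate variables are not named.
- Regression: "Multivariable logistic regression analysis was performed to detect associated factors with PWV and AIx@75". The covariates, the population and the cut-points are not named, and EFT and cIMT are not covered.

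The significance rule is "p<0.05 was considered as a statistically significant value". There is no sample-size or power statement.

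**The concern.** The design is cross-sectional, so years since diagnosis is the only time axis the study has. With ages 8 to 18 and no upper limit on duration, the criteria allow exposures from 2 years to more than 10. The two-group test gives one average over whatever mix of durations consecutive recruitment produced. If vascular change accumulates, that average overstates the difference for recently eligible children and understates it for those with long exposure, and a reader cannot tell which children it describes.

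The comparison also leaves out age. The controls are age-matched, so age should not bias the contrast, but age-related spread in the markers stays in the error term of an unadjusted test.

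The other listed analyses do not clearly fill the gap, even if duration is among their variables. A Spearman coefficient within patients gives no difference from controls, and unadjusted it mixes duration with age, because older children can have had T1DM for longer. Kruskal–Wallis across duration strata would bring in controls but would not adjust for age. Logistic regression is stated for only two of the four markers and needs a dichotomised outcome.

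**Working it through.** **Inputs from the document.** 87 controls; age 8–18; duration at least 2 years; significance level 0.05 (two-sided assumed). The plan states no power or effect size, so there is no figure of its own to reproduce.

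**Assumed inputs.** 87 patients; marker SD 1; mean difference 0.30 SD; marker-age correlation ρ of 0.3 or 0.5; ages uniform over 8–18; several duration distributions with means from 4.0 to 7.0 years. None of these is in the document.

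**Step 1: group difference, unadjusted and age-adjusted.** The standard error is √(2/87) = 0.1516 SD. Power is Φ(d/SE − 1.96).

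- Unadjusted: 0.30/0.1516 = 1.98, power 51%.
- Adjusted for age, residual SD √(1 − ρ²): for ρ = 0.3 it is 0.954, so d = 0.314, z = 2.07, power 55%. For ρ = 0.5 it is 0.866, so d = 0.346, z = 2.28, power 63%.

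Simulation agrees: 47–53% for the t-test and 53–64% for the age-adjusted group term. With centred duration also in the model, the T1DM term has 53–65%. The gain in that term therefore comes from age; adding duration leaves it essentially unchanged.

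**Step 2: the duration slope.** Take an effect proportional to years, with onset uniform between age 1 and 2 years before the visit: mean duration 7.0, SD 3.33, age-duration correlation r = 0.43. With the controls helping to fix the age slope, z = (0.30/7.0) × 3.33 × √87 × √(1 − r²/2) / √(1 − ρ²).

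- ρ = 0.3: z = 1.33, power 26%.
- ρ = 0.5: z = 1.46, power 31%.

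Across the assumed duration patterns, simulation gives about 23–34%. Keeping controls in the model raises the information on the slope by the factor (1 − r²/2)/(1 − r²), about 11% at r = 0.43 and 31% at r = 0.62.

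**Step 3: a single years-of-T1DM term (0 in controls).** With equal groups, its squared correlation with group status is E = m²/(m² + 2v), where m and v are the mean and variance of duration. For durations uniform over 2–10 years, m = 6 and v = 5.33, so E = 36/46.67 = 0.77. If the effect is proportional to years, this term multiplies the group test's z by 1/√E. If the effect is flat, it multiplies it by √E. At 0.425 SD, where the group test has 80% power (z = 2.80):

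- Proportional: 2.80/0.878 = 3.19, power 89%.
- Flat: 2.80 × 0.878 = 2.46, power 69%.

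Simulation gives 89% and 68%. At 0.30 SD with age adjustment, it gives about 66–76% if the effect accumulates and about 39–50% if it is flat, against 54–63% for the age-adjusted group test in the flat case.

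**Step 4: what the average describes.** For an effect proportional to years and durations uniform over 2–10, the pooled difference is the 6-year effect: 6/2 = 3 times the 2-year effect and 6/10 = 60% of the 10-year effect. For mean durations of 7.0 and 4.0 years, the same per-year effect gives averages that differ by 7.0/4.0 = 1.75. These ratios follow from the assumed proportionality; they are not findings about this sample.

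**The case against.** The planned comparison is not wrong. It estimates the average difference in consecutively recruited eligible patients, and leaving duration out does not inflate the type I error. Variation around an average is not bias, and the title asks about risk in children with T1DM rather than about dose-response. All of this stands.

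The document is a short summary. Only two groups are recruited, so the mention of Kruskal–Wallis implies subgroups, and duration strata with controls is one possibility. The logistic model could include all children and duration. A reader might therefore infer too much in saying that duration was left out of the analysis; the text shows only that no analysis is committed to it. This narrows the point but does not remove it.

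The effect may also be flat after 2 years. A model that keeps T1DM status and adds centred duration then loses one degree of freedom, whereas the single years-of-T1DM term loses real power (Step 3). That term should not carry the main inference.

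Finally, long durations are permitted but not reported. With durations of 2 years plus an exponential of mean 2 years, the share at 10 or more years is exp(−8/2) = 1.8% before the limit set by age, or one or two children in 87. A 10-year estimate would then be near-extrapolation.

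**Conclusion.** The point holds as a gap in specification and efficiency. Duration is used only as an entry rule, the stated two-group test uses neither age nor duration, and no listed analysis is committed to estimating the patient-control difference by duration. With an assumed 87 per group and 0.30 SD, age adjustment takes power for the group difference from about 50% to 53–65%. The duration term contributes an otherwise missing estimate, with only about 23–34% power.

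Two stronger readings are tempting and are not supported. One is that pooling necessarily dilutes a real effect: that requires an effect that keeps growing after 2 years, and the document gives neither its shape nor the duration distribution. The other is that modelling duration would lift power to 66–76%: that figure belongs to the single years-of-T1DM term under an accumulating effect, and it falls to 39–50% if the effect is flat.

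**What to change.** Keep the t-test or Mann–Whitney comparison. Add to the Statistical analysis section, for each of EFT, cIMT, PWV and AIx@75, one linear model in all children, on a transformed scale if the marker is skewed:

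marker = T1DM status + T1DM × (years since diagnosis − patient mean) + age + sex.

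Report the T1DM-control difference at the mean duration and at chosen durations within the observed range, each with a 95% interval. Present the duration slope as an estimate with its interval, not as a significance verdict. A single years-of-T1DM term (0 in controls), adjusted for age and sex, may be shown only as a labelled sensitivity analysis. State also whether duration enters the Kruskal–Wallis groups, the Spearman variables and the logistic covariates.

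The cost is a few sentences and one extra SPSS model per marker. No new measurement should be needed, because applying the 2-year rule requires knowing when T1DM was diagnosed.

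### Controls are matched on sex, age and BMI, but the stated group tests ignore those factors; this costs precision and power, not validity

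*Combined protocol and SAP*

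**What the plan says.** In the Combined protocol and SAP, the Study Protocol section states: "The control group consisted of 87 sex, age and BMI matched healthy children". It does not say whether matching was by individual pair or at group level, nor the ratio or tolerance. Patients "were consecutively included in the study", with no total given. Their BMI criterion is age- and sex-specific ("T1DM patients with a body mass index (BMI) between the 5th and 85th percentile according to age and gender"), and the matching variables are available for everyone ("Each subjects weight, height measurements were done and BMI was estimated").

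For the group comparison, the Statistical analysis section states: "Numerical variables with and without normal distribution were compared using the independent samples t-test and Mann–Whitney U, respectively". The Kruskal–Wallis test is given for more than two groups. No paired test, matched-set term or covariate-adjusted group comparison is named.

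Two further analyses touch the outcomes:
- "Spearman correlation analysis was performed to determine the variables associated with EFT, cIMT, AIx@75, and PWV scores". This is also unadjusted.
- "Multivariable logistic regression analysis was performed to detect associated factors with PWV and AIx@75". Its terms, its population and the cut-offs that make these outcomes binary are not stated, and it does not cover cIMT or EFT.

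**The concern.** Matching on a prognostic factor makes the two groups more alike on it, so the difference between them varies less from sample to sample. An unpaired, unadjusted test does not know this: it puts all the outcome variance explained by age, sex and BMI into the error term. With close matching, the precision gained by design is therefore not credited in the standard error. With loose matching, much of that precision was never gained, and an adjusted model would recover it.

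At stake is sensitivity. A real, moderate T1DM–control difference in a vascular or cardiac marker is more likely to be reported as non-significant, with no adjusted estimate or confidence interval to show what the data were compatible with.

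**Working it through.** **Inputs.** From the documents: 87 controls, matching on sex, age and BMI, patient ages 8–18, significance at p<0.05. Assumed: two-sided testing, 87 patients, a true difference of 0.35 SD, and R2 of 0, 0.10 or 0.25. The plan gives no power or sample-size figure to reproduce.

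**Close matching, closed form (outcome SD units).**
- SE used by the unpaired test: sqrt(2/87) = 0.1516.
- True SD of the raw difference: 0.1516 × sqrt(1 − R2) = 0.1438 at R2 = 0.10 and 0.1313 at 0.25.
- Reported SE over true SD: 1/sqrt(1 − R2) = 1.054 and 1.155.
- Actual type I error: 2 × (1 − Φ(1.96/sqrt(1 − R2))) = 0.039 and 0.024, against a nominal 0.05.
- Power of the t-test: the rejection limit is 1.974 × 0.1516 = 0.299, so power is Φ((0.35 − 0.299)/true SD), about 64% and 65%.
- Power when adjusted: Φ(0.35/true SD − 1.974), about 68% and 76%.

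**Simulation.** 8000 data sets per cell, 87 per group. Age was uniform on 8–18, sex binary and BMI normal, carrying 60/10/30% of R2. Close matching means that the control has the patient's sex, with age and BMI differing by 0.1 SD noise. Loose matching means independent samples kept only if each factor has p>0.05. Simulation error is about 0.5 points in power and 0.002 in type I error.

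| Matching | R2 | True SD raw / adjusted | t-test type I error | Power: t-test / Mann–Whitney / adjusted |
|---|---|---|---|---|
| Close | 0 | 0.151 / 0.151 | 0.047 | 62.9 / 60.9 / 62.9% |
| Close | 0.10 | 0.143 / 0.143 | 0.037 | 63.1 / 60.1 / 66.8% |
| Close | 0.25 | 0.132 / 0.132 | 0.024 | 64.8 / 62.1 / 74.8% |
| Loose | 0 | 0.151 / 0.152 | 0.048 | 63.2 / 61.1 / 62.5% |
| Loose | 0.10 | 0.149 / 0.144 | 0.044 | 63.9 / 62.1 / 67.0% |
| Loose | 0.25 | 0.147 / 0.132 | 0.042 | 64.0 / 60.8 / 75.7% |

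The gain over the t-test is 66.8 − 63.1 = 3.7 and 74.8 − 64.8 = 10.0 points with close matching, and 67.0 − 63.9 = 3.1 and 75.7 − 64.0 = 11.7 with loose matching. The adjusted test keeps type I error between 0.047 and 0.051 in these cells. With loose matching, the residual shift of the raw difference has a median of 0.03 SD and a 95th percentile of 0.08 SD at R2 = 0.10, and 0.05 and 0.13 SD at 0.25.

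**Tight frequency matching.** This is matching at group level, but it behaves like pairing. In a separate simulation (3000 runs, one composite covariate, R2 = 0.3), the raw and adjusted estimates were almost equally variable (0.129 and 0.127) while the t-test still reported 0.151, with type I error 0.023. What matters is therefore how close the matching was, not whether it was by pair or by group.

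**Other patient numbers (loose matching, 5000 data sets).** t-test versus adjusted power is 54% v 58% (R2 = 0.10) and 55% v 66% (0.25) with 60 patients. With 120 patients it is 70% v 74% and 70% v 81%.

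**Skewed outcomes.** The table uses normal data, whereas the plan keeps Mann–Whitney for non-normal variables. With lognormal data (log-SD 0.8, 0.35 SD shift on the log scale), Mann–Whitney gave 62/60/62% at R2 = 0/0.10/0.25, against 48/53/58% for a raw-scale linear model with robust standard errors. In a similar run of 2000 data sets, a log-scale model gave 62/65/77% against 60/61/62% for Mann–Whitney; the log scale was exactly right there by construction. With heavy tails (t, 3 df), Mann–Whitney beat the linear model at R2 = 0 and 0.10 (88% and 83% v 67% and 70%) and was level at 0.25.

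**The case against.** The strongest reply is that nothing invalid has been done. Matching already limits confounding by these three factors, the unadjusted test is valid or conservative, and the benefit of adjusting rests on an R2 that the documents do not give. That stands, and it makes this a point about efficiency and estimation only. Two details of the simulation are also arbitrary: the split of R2 between the factors, and an untruncated BMI although patients are restricted by percentile.

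It can also be said that the logistic regression already adjusts. For PWV and AIx@75 it may. It is not described as containing diabetes group or the matching factors, but nothing excludes them. It offers nothing for cIMT or EFT.

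A third reply is that a linear model is not always better than a rank test. This also stands: under marked skew or heavy tails a raw-scale model can lose to Mann–Whitney, so the rank test should not simply be dropped.

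A reader might infer more than the documents support:
- That the unmodelled matching produces false positives. The direction is the opposite.
- That a paired test is required. The text never says that controls were individually paired.
- That the loss is large. At R2 = 0.50 the simulated gain would be 22–26 points, but nothing in the documents points to an R2 of that size.

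**Conclusion.** The point holds as a loss of precision and power. It is worth fixing because the remedy is nearly free, not because the stated tests are wrong. Close matching makes the unadjusted SE too wide; loose matching leaves the raw estimate noisier than it need be; real matching may lie anywhere between. The gain of 0, 3–4 or 10–12 points at R2 = 0, 0.10 or 0.25 rests on 87 patients, a 0.35 SD difference and approximately normal outcomes. The actual gain is unknown and may differ between the four outcomes. The statement that no adjusted analysis is described is firm only for cIMT and EFT.

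**What to change.** For each of PWV, AIx@75, cIMT and EFT, add a linear model with group, age, sex and BMI (as percentile or SDS), and report the adjusted T1DM–control difference with its 95% CI.

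- Use a log or other suitable transformed scale if the outcome is skewed.
- Include a pair effect only if controls were individually paired; a sentence on how matching was done settles this.
- Where an outcome stays markedly skewed or heavy-tailed, keep Mann–Whitney alongside the model or use a covariate-adjusted rank analysis. Do not rely on a raw-scale model with robust standard errors there.
- The text is in the past tense, so label the model post hoc if the data have already been analysed.

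The cost is one extra model per outcome and about three degrees of freedom, with no new data. If R2 is near zero, almost nothing is lost: 62.5% adjusted against 63.2% unadjusted power at R2 = 0 with loose matching, a gap about the size of the simulation error.
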